2. To identify patient and physician behaviors associated with GERD symptom improvement.

Design and Outcomes

This is a randomized controlled trial to assess the physiologic and behavioral mechanisms associated with augmented medication effects in adult patients with functional GERD-related symptoms.

Subjects will be randomized to receive one of two different semi-scripted visit types – either a “standard visit” modeled after an empathic, conventional primary care evaluation or an “expanded visit” modeled after an integrative medicine consultation. During the visit, we will measure heart rate variability (HRV) and galvanic skin response (GSR) in the patient-provider dyads; in addition, we will video record the interactions for later

analysis of behavioral responses. Subjects will receive a two-month supply of amitriptyline (10 mg/day) or omeprazole (20 mg/day, depending upon the nature of their GERD symptoms), along with instructions for taking it. Following the visit, subjects will complete questions assessing their relationship/rapport with the study provider. Subjects will complete a daily GERD symptom diary during the first and eighth weeks of the study. At the end of the 8-week observation period, they will complete follow-up measures of GERD symptom severity and quality of life.

Interventions and Duration

Subjects will have a single visit with a “study provider,” a physician or nurse practitioner who they have never previously met. Subjects will complete a daily symptom diary for the 1st and 8th weeks following this visit and return for a second study visit in which they will complete questionnaires and be debriefed by a member of the study team.

Sample Size and Population

We plan to enroll 60 subjects with functional GERD, age 24-70 with heartburn symptoms 3 or more days per week. Thirty subjects will be randomized to the expanded visit intervention and 30 subjects will be randomized to the standard visit intervention (1:1 expanded vs. standard randomization). We will also enroll approximately 5-6 physicians or nurse practitioners and stratify randomization by study provider such that each provider will see 10-12 subjects (5-6 expanded visits and 5-6 standard visits).

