5.2 Handling of Study Interventions

To minimize potential bias that could affect study staff interactions with subjects, the subject will be randomized immediately before the study visit and the study provider will receive the appropriate study visit script. At the time of consent, study subjects will not be informed about the two different interview types or that part of the study involves testing the effect of the doctor-patient interaction on response to treatment. Concealment of these aspects of the study protocol is essential to maintaining the validity of the study as data suggests that patients' responses change when they know that the doctor-patient interaction is being studied^{69,70}. The study PI, or another study team member, will notify subjects at their follow-up study visit, after the exit interview, that there were two possible types of physician visits, that this aspect of the study was concealed from them initially, and of the rationale for doing so. A script outlining this planned debriefing is present in Appendix F. We believe that this intervention is minimal risk and that our plan meets the federal criteria for permitting alteration of some elements of informed consent⁷².

Subjects will be informed about taking amitriptyline or omeprazole as part of the study during the consent process and the study physician will discuss this with them during the study visit. Subjects will receive a container with an 8 week supply of the medication from a study team member at the end of the study visit.

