5.4 Adherence Assessment

Subject adherence is defined by subjects completing at least 6 out of 7 days of their daily symptom diary during the last week of the study period and taking amitriptyline

or omeprazole at least 6 out of 7 days during that week. Adherence will be assessed when subjects return their symptom diaries at their follow-up visit. For subjects who return incomplete symptom diaries, average daily symptom severity for the days completed will be calculated. If there is insufficient data to make this calculation, we will assume that symptoms are unchanged from baseline.

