6.2.5 Post-Intervention Measures (Day 0)

Immediately following the study physician visit, subjects will be asked to complete the following questionnaires:

- Impressions of the Study Physician questionnaire – a 4 item measure assessing the patient’s impression of the study physician including overall rating of the physician, satisfaction with the physician, willingness to recommend the physician to others, and desire to see the physician again.
- Consultation and Relational Empathy questionnaire (CARE) – a validated and commonly used 10 item measure for assessing the quality of the patient encounter and perceptions of empathy from the treatment provider⁸⁰. I used it in my pilot study.
- HEAL Patient-Provider Connection – a subset of the Healing Encounters and Attitudes, a recently validated 7-item measure of the patient-provider connection. This is a patient-reported outcome developed as part of a set of tools to measure non-specific factors in treatment using the NIH PROMIS methodology⁸¹.
- Current Stress Question – 1 item self-report measure of current stress level on a scale of 0 (no stress) to 10 (extreme stress)

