6.2.6 Telephone Check-in

Study coordinators will call enrolled subjects who have completed study visit 1 twice to check in. The first time will be approximately 1 week after the first study visit and the second time 1 week before the second study visit. These telephone check-ins will 1) serve as a reminder to participants to complete their daily symptom diary, 2) remind participants to take the medication as prescribed 3) address any participant questions or concerns, and 4) remind/confirm participants’ second study visit appointment.

Participants who wish to discontinue the study medication and unenroll from the study will be directed to speak with the study PI to receive instructions for tapering off of the medication if they have not done so already.

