8. INTERVENTION DISCONTINUATION

Subjects who decline to participate in study procedures (e.g., completion of study questionnaires, physiologic monitoring, and/or video recording) will be terminated from the study without further follow-up. Any subjects who are disruptive or felt to pose a threat to study staff will also be terminated without follow-up. If a subject experiences an adverse reaction to amitriptyline or omeprazole and decides to stop taking the medication, or if a study physician deems it in the subject's best interest to stop the medication, the subject will continue to be followed for the duration of their initially planned participation (out to 8 weeks), unless the subject declines to participate further.

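### Section 8 ends contact with subjects the team terminates, even after the 8-week drug supply is dispensed; a closing safety call should be required

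*Combined protocol and SAP*

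**What the plan says.** Section 8 (Intervention Discontinuation) sets three rules.

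- **Declining procedures.** Its examples are questionnaires, monitoring and video. Subjects who decline "physiologic monitoring, and/or video recording) will be terminated from the study without further follow-up".
- **Disruption or threat.** "Any subjects who are disruptive or felt to pose a threat to study staff will also be terminated without follow-up".
- **Adverse reaction.** If the subject stops the drug because of a reaction, or a study physician decides it should stop, "the subject will continue to be followed for the duration of their initially planned participation (out to 8 weeks", unless the subject no longer wishes to take part.

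The first two rules mention neither timing nor drug already in the subject's hands.

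Under Section 5.2 the subject receives an "8 week supply of the medication from a study team member at the end of the study visit". The précis (Design and Outcomes) words the quantity differently: "Subjects will receive a two-month supply of amitriptyline (10 mg/day) or omeprazole". Section 5.1 gives one dose a day: amitriptyline 10 mg at bedtime or omeprazole 20 mg on waking.

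On later contact, Section 6.2.6 says "Study coordinators will call enrolled subjects who have completed study visit 1 twice to check in". The calls fall about one week after Visit 1 and one week before Visit 2. Section 7.3 states that health concerns are recorded at these calls only if the subject raises them. Staff ask about adverse events at Visit 2, Day 53 to 60 (Sections 6.1, 6.27, 7.2 and 7.3).

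**The concern.** A subject can be removed by the team while holding most of the drug supply. Read literally, the first two rules of Section 8 then end all contact, including the one visit at which staff ask about adverse events. The third rule treats drug exposure as a reason to keep following a subject who has stopped the drug. A terminated subject who may still be taking it gets no such follow-up.

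The stake is individual safety. Section 7 lists conduction changes, serotonin syndrome and suicidal ideation as rare effects of amitriptyline, and agitation as a less common one. A reaction that is unrecognised at termination, or that starts later, would come to light only if the subject phoned. Agitation might also be what staff see as disruption, and Section 8 does not say which of its rules then applies.

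**Working it through.** The plan gives no figure for this point, so the check is a reading of the text followed by a count of doses and contacts.

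**Step 1. Who can be terminated after dispensing?**

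- Refusal of physiologic monitoring or video arises during the provider visit, before the drug is handed over. It falls outside the concern.
- Incomplete diaries are not named as a ground for termination. Section 5.4 handles them in the analysis: "average daily symptom severity for the days completed will be calculated".
- Refusal of the post-visit questionnaires is possible on Day 0. Section 6.2.5 says "Immediately following the study physician visit, subjects will be asked to complete the following questionnaires", but the order of questionnaires and dispensing is not stated.
- Disruption can occur at the end of Visit 1, at a check-in call or at Visit 2. Refusal at a check-in call or at Visit 2 is also possible.

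**Step 2. Which provisions reach a subject the team terminates who has not asked to stop the drug?**

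| Provision | Whom it covers | Reaches this subject? |
|---|---|---|
| 6.2.6, taper instructions from the study lead | Those who wish to stop the drug and leave | No |
| 6.27, taper instructions and adverse-event questions | Those seen, or contacted remotely, for Visit 2 | Not if terminated earlier |
| 7 and 7.2, physician advice | Those who phone, or who raise a concern at the week-1 call | Only if the subject speaks up |
| 7.4 and 7.5, reporting and follow-up | Events already recognised or phoned in | Only for those events |

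No row gives this subject a scheduled contact or drug instructions after termination.

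**Step 3. How much drug and how many contacts are left?**

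Inputs: 8 weeks × 7 = 56 doses. Full adherence is assumed, so Day d means d doses taken, up to the supply. Check-in 2 is 7 days before Visit 2: 53 − 7 = Day 46 to 60 − 7 = Day 53. Scheduled contacts after dispensing are check-in 1 + check-in 2 + Visit 2 = 3, of which 1 (Visit 2) is a solicited adverse-event query.

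| Terminated at | Doses left of 56 | Contacts begun (of 3) | Solicited queries (of 1) |
|---|---|---|---|
| Day 0, after dispensing | 56 − 0 = 56 (100%) | 0 | 0 |
| Check-in 1, about Day 7 | 56 − 7 = 49 (87.5%) | 1 | 0 |
| Check-in 2, Day 46 to 53 | 56 − 46 = 10 (17.9%) to 56 − 53 = 3 (5.4%) | 2 | 0 |
| Visit 2, Day 53 to 60 | 56 − 53 = 3, down to 0 | 3 | At most 1 |

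The Day 0 supply is 56 × 10 mg = 560 mg of amitriptyline or 56 × 20 mg = 1,120 mg of omeprazole. If the précis wording means 60 doses (an assumption), the remainders are 60; 60 − 7 = 53; 60 − 46 = 14 to 60 − 53 = 7; and 7 down to 0. On either count the exposure lies between the end of Visit 1 and the early weeks.

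**The case against.** The strongest reply is that almost nobody is affected and that the safeguards are better than Section 8 alone suggests. A physician discusses the drug's risks at consent. The provider gives scripted advice on taking it and what to expect (Section 5.1). Many subjects are recruited through a gastroenterology clinic and probably remain under usual care. Callers with side effects reach a study physician. Staff report even possible adverse events (Section 7.4), and known events are followed until they settle (Section 7.5). If a physician judges that a disruptive subject should stop the drug, the third rule of Section 8 already keeps that subject in follow-up. The no-follow-up wording may also have been meant only for research follow-up.

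Much of this stands. It limits the reach and supports a low severity. A reader might infer that every subject terminated under Section 8 is left without taper instructions. That is wrong: someone who declines procedures because they want to stop the drug and leave is covered by Section 6.2.6. Nor can all 56 doses be attributed to a subject who refuses the Day 0 questionnaires, since the drug might not yet have been handed over.

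The reply does not supply a closing query or drug instructions for a subject removed by the team who has not asked to stop. The remaining routes need the subject to speak up or an event to have been recognised. The benign reading of the wording is reasonable, but Section 8 does not state it.

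**Conclusion.** The point holds in a narrow form, as a cheap improvement of low severity. It applies to subjects terminated by the team after dispensing who have not themselves asked to stop the drug. These would mainly be cases of disruption or questionnaire refusal between the end of Visit 1 and the early weeks. They lose the one solicited adverse-event query and have no assigned stop or taper instructions.

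The dose counts assume daily dosing with full adherence. They measure supply, not risk. The documents give no number of such terminations and none is assumed. A reader might infer that harm is likely, but the text does not support that: Section 7 describes low-dose amitriptyline with the most vulnerable excluded, and omeprazole as generally well tolerated. The finding does not touch the sample size or the primary analysis.

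A reader might also infer that the study has no provision for these subjects at all. That cannot be concluded. Appendix G (the safety monitoring plan, cited in Section 7.6), the visit scripts in Appendix E and the consent pages were not available, and any of them may address it.

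**What to change.** Amend Section 8 as follows.

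1. State that ending follow-up applies to research procedures only.
2. For anyone terminated after dispensing, require one remote closing safety contact unless the subject refuses it. It should ask the adverse-event questions of Section 7.3 and give stop or taper instructions for the remaining supply. Section 6.27 already describes a telephone or video call for adverse-event data when a subject cannot safely attend Visit 2, and the same call can be used, so staff need not meet a threatening subject in person.
3. State that if disruptive behaviour after dispensing is judged drug-related, the adverse-reaction rule of Section 8 governs.

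Further safety checks to week 8 are optional. If Appendix G already provides this, a cross-reference that brings Section 8 into line is enough.

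The cost is two or three sentences and an occasional call by existing staff. The downside is that a few of those calls will go to unwilling or difficult subjects.

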9. STATISTICAL CONSIDERATIONS

9.1 General Design Issues

Design: This is a single-blinded randomized controlled trial in which subjects will be randomized in a 1:1 fashion to receive either an expanded or standard visit with a healthcare provider about their GERD symptoms and then treated with amitriptyline or omeprazole for 8 weeks to determine whether an expanded visit can augment the effects of a medication compared to a standard visit.

Primary hypotheses:

1. Subjects who receive an expanded visit will have a greater improvement in their GERD symptoms after 8 weeks of treatment with amitriptyline or omeprazole compared to subjects who receive a standard visit.

Secondary hypothesis:

1. Patient-provider dyads in expanded visits will have a greater percentage of the total visit time spent in physiologic concordance (measured by either GSR or HRV) compared patient-provider dyads in standard visits.
2. Percentage of visit time with physiologic concordance (in GSR or HRV) will be correlated with GERD symptom improvement.
3. Subjects who experience physiologic changes similar to those elicited by mind-body techniques (i.e., decreased GSR and increased high frequency HRV) over the course of their visit (first several minutes compared to the last several minutes of the visit) will demonstrate greater improvements in GERD symptom severity than subjects who do not.

4. Healthcare providers in expanded visits will demonstrate more patient-centered non-verbal behaviors (e.g., smiles and gazes) and global impression (e.g., engaged, friendly, relaxed) compared to providers in standard visits as rated by blinded reviews of thin slices of video excerpts.
5. Patient and provider smiling at the end of study visits will be significantly associated with GERD symptom improvement 8 weeks later.

Primary outcome:

1. Change in the average daily GERD symptom severity score from baseline to the last week of the study in the expanded vs. standard group. GERD symptom severity is based on the sum of scores assessing the severity of daytime heartburn, nighttime heartburn, and acid reflux each on a 0-4 point scale (none, mild, moderate, severe, very severe; higher scores signify worse symptoms).

Secondary outcomes:

1. Ratio of the sum of positive correlations over the sum of negative correlations in GSR (or HRV) across patient-provider encounters for standard vs. expanded visit types and for responders vs. non-responders (those with a 50% or greater improvement in their GERD symptom severity).
2. Absolute change in GSR (or high frequency HRV signal) in patient recordings from the beginning of the study visit to the end of the study visit and correlation with subsequent change in GERD symptom severity.
3. Differences in blinded ratings of 2 minute thin slices of study visit videos from the beginning to the end of the study in supportive global impressions (e.g., engagement, relaxed, patient seems pleased/satisfied) and non-verbal behaviors (e.g., smiling) between standard and expanded visit types and correlation with subsequent change in GERD symptom severity.

Validity and reliability of outcome measures:

1. Assessment of physiologic concordance has been described by a number of groups and we will be using similar methodology^{45,82}.
2. GERD symptom severity will be assessed by a daily symptom diary used by a number of other groups in medication trials and in our previous study^{64,83,84}. The average daily GERD symptom severity is based on the daily sum of scores from the first three questions assessing severity of daytime heartburn, nighttime heartburn, and acid reflux averaged over a 7 day period. The change in GERD symptom severity is calculated by subtracting the average daily GERD symptom severity score during the last 7 days of the study from the average daily GERD symptom severity score at study enrollment. The other GERD symptom questionnaires we are using have also been validated^{26,73,74}.
3. Social psychologists have developed and validated a variety of coding schemes to analyze providers' verbal and non-verbal behaviors and to link these behaviors with patient satisfaction, understanding, trust, rapport, empathy, and a variety of related factors^{9,58-63}. We will use a subset of these validated coding

schemes. Thin slices have shown high reliability and validity for behaviors such as gaze, nods, and smiles⁸⁵.

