1.1 Primary Objective

To determine in a randomized controlled trial whether an expanded, compared to a standard, provider visit can augment the effects of a medication targeting functional GERD symptoms.

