Social psychologists have developed and validated a variety of coding schemes to analyze providers’ verbal and non-verbal behaviors and to link these behaviors with patient satisfaction, understanding, trust, rapport, empathy, and a variety of related factors^{9,58-63}. This rich literature has yielded many insights and a variety of tools used in studies of physician-patient communication, but rarely have these tools been linked with physiology or health outcomes⁷.

[name] recently observed that an “expanded” provider visit modeled after a visit to an IM provider was more effective in decreasing heartburn and dyspepsia symptoms in patients with GERD than a “standard” provider visit modeled after an empathic conventional medical visit⁶⁴. This study used a script of pre-determined questions for each visit type. The standard visit script included questions about GERD history, symptoms, prior evaluation and treatments, and past medical history. The expanded visit script included the same questions plus additional questions that inquired about their GI symptoms, non-GI symptoms, and overall temperament. Thus, the main differences between the visits were the length of time spent with the subject and the additional questions that were asked. Many of the subjects in this study were already taking pharmaceutical medications for GERD, suggesting that symptom improvement resulting from the expanded provider visit may enhance the efficacy of some medications in providing adequate symptom relief. We intend to formally test this hypothesis, that augmented patient-provider visits can enhance medication-related benefits, in this current study.

While some may argue that increasing visit length is impractical in conventional healthcare settings, one reason why payers will not adequately reimburse for increased visit lengths is the lack of data linking visit length with health outcomes. Increased visit length has been associated in clinical practice with reduced number of prescriptions and increased patient satisfaction, engagement, and quality of care⁶⁵⁻⁶⁷. Other studies suggest mechanisms by which provider communication (verbal & non-verbal) may affect health outcomes⁶⁸. Yet we really do not know what makes longer visits more effective. By better understanding the mechanisms that make the expanded visit intervention effective, we will be able to make informed decisions

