Once enrolled, subjects will be randomized to receive either the standard visit intervention (n=30) or the expanded visit intervention (n=30). They will not know that there are two possible visit choices. This aspect will be revealed to subjects during a debriefing at the follow-up visit at the end of their participation in the study. We will stratify by provider and create permuted block sizes of 2 and 4 with the intent to enroll 5-6 providers who will each see 10-12 subjects. If a provider cannot commit to this many

visits, the study biostatistician may need to adjust the randomization scheme and we will consent additional providers.

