5. STUDY INTERVENTIONS

5.1 Interventions, Administration, and Duration

Subjects will be randomized to receive either a “standard visit” or an “expanded visit” with a study provider. The standard visit is based on a high quality, empathic, conventional primary care encounter. The expanded visit is based on an integrative medicine consultation. Both visits are based on a script of questions and statements to the patient/subject (see Appendix E). The standard visit script includes questions about GERD history, symptoms, prior evaluation and treatments, and past medical history as well as a brief physical exam. The expanded visit script includes the same questions as the standard visit script plus additional questions that inquire about the modalities of their GI symptoms (e.g., nature of the reflux taste, sensation of heartburn pain and/or abdominal fullness, time of day better/worse), details about non-GI symptoms, quality of sleep, the effect of the weather on symptoms, food cravings and aversions, menstrual flow, fears/phobias, and overall temperament. In this way, the expanded visit tries to understand the patient’s/subject’s constitution in a way that many systems of integrative medicine attempt to do. To reduce the potential for introducing bias by using the words “standard” and “expanded”, the visit templates that the study providers will follow will simply refer to the number of questions to be asked on the template (e.g., 6 Question Template).

At the end of both the standard and expanded visits, the provider will recommend the subject take the study medication and describe how to take it and what to expect. Subjects will receive the same scripted advice in both groups. Each subject will receive an 8-week supply of amitriptyline or omeprazole with instructions for how to take it (10 mg daily at bedtime or 20 mg daily when waking up, respectively).

In our pilot study⁶⁴ we did not limit the amount of time spent with the study subject. On average, the standard visit lasted 18 minutes (range 11-32 minutes) and the expanded visit lasted 42 minutes (range 23-74 minutes). The study providers will be instructed to maintain equal empathy in both groups (e.g., kind and friendly manner, maintain eye contact, active listening and repeating back the patient’s words, expressions of empathy). Thus, the main differences between the visits will be the length of time spent with the subject and the additional questions that are asked.

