12. POTENTIAL BENEFITS

12.1 Potential Benefits to Participating Individuals

Study subjects (“patients”) may experience improvement in their GERD symptoms by participating in this study. The placebo response in GERD-related trials may be as high as 40% [35] and our prior data suggests that a therapeutic encounter such as the expanded visit can result in at least temporary symptom improvement for some individuals [61]. In addition, subjects may also experience improvement in their GERD symptoms from taking amitriptyline or omeprazole. It is also possible that subjects may not experience any direct benefit from participating in this study. Subjects will receive \$30 and a 2 month supply of amitriptyline or omeprazole for participating in the first study visit and \$50 for attending the second study visit.

Participating study providers will also be remunerated for their time (\$80.00 per visit) and may benefit by learning skills for relating to patients more effectively.

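### Every patient is medicated and only visit type is randomised, so the trial can show a benefit of the expanded visit in medicated patients but not that the visit enhances the drug effect

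*Combined protocol and SAP*

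**What the plan says.** The aim is worded as augmentation of a drug effect in several places. Section 1.1 asks whether the expanded visit can "augment the effects of a medication targeting functional GERD symptoms". The Primary Aim in the Précis uses similar words, covering traditional as well as functional symptoms. The Design and Outcomes paragraph of the Précis speaks of mechanisms behind increased medication effects. The design paragraph of 9.1 gives the purpose as "to determine whether an expanded visit can augment the effects of a medication compared to a standard visit". Section 2.2 is the most explicit: "We intend to formally test this hypothesis, that augmented patient-provider visits can enhance medication-related benefits, in this current study".

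The primary hypothesis in 9.1 is narrower: "Subjects who receive an expanded visit will have a greater improvement in their GERD symptoms after 8 weeks of treatment with amitriptyline or omeprazole", compared with those given a standard visit. Secondary objective 2 in 1.2 is likewise a plain comparison of symptom improvement between visit types.

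On the design itself, section 4.3 randomises visit type only, 30 to each arm, stratified by provider. Section 5.1 says: "Each subject will receive an 8-week supply of amitriptyline or omeprazole with instructions for how to take it". Section 5.3.2 lists the medication as required, and 4.3 has the drug follow diagnosis and treatment plan. No placebo or untreated arm is described. The primary ANCOVA in 9.5.1 contains baseline severity and visit type.

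**The concern.** To say that a visit enhances the benefit of a drug is to say that the drug's effect is larger under one visit type than under the other. Showing that requires an estimate of the drug's effect under each visit, and so patients with and without the drug under each. This trial has only patients with it.

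At stake is the headline conclusion. If the primary test is positive and is reported against the aim as worded, the natural statement is that longer visits make these drugs work better. The data would support only that patients on these drugs did better after the expanded visit.

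**Working it through.** **The plan's own figure.** Section 9.2 gives minimal detectable differences (MDDs) for 30 per arm, 80% power and two-sided alpha 0.05.

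- Normal approximation: MDD = (1.960 + 0.842) × SD × √(2/30). At SD 1.5 this is 2.802 × 1.5 × 0.2582 = 1.085. At SD 2.0 and 2.5 it is 1.447 and 1.808.
- Noncentral t, 58 degrees of freedom: 1.103, 1.471 and 1.839, against the tabulated 1.10, 1.47 and 1.84.

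The table reproduces. It refers to the difference between visit groups.

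**What that difference contains.** Let V = 1 for the expanded visit and M = 1 for study medication, and write mean improvement as b0 + b1·V + b2·M + b3·V·M. Here b1 is the effect of the visit without the drug, b2 the drug effect under a standard visit, and b3 the enhancement of the drug effect by the visit. Since M = 1 for everyone:

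- standard arm: b0 + b2
- expanded arm: b0 + b1 + b2 + b3
- difference: b1 + b3

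Two arm means cannot determine four parameters; the design matrix has rank 2. Only the sum b1 + b3 is estimable, and adjusting for baseline severity does not alter that. Each of these rows gives the same observed difference:

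| b1 (visit alone) | b3 (enhancement) | Difference |
|---|---|---|
| 1.10 | 0 | 1.10 |
| 0 | 1.10 | 1.10 |
| 0.55 | 0.55 | 1.10 |
| 1.50 | −0.40 | 1.10 |

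In the last row the visit reduces the drug effect, yet the primary result is unchanged.

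**Whether anything else in the plan supplies the missing contrast.**

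- Amitriptyline versus omeprazole patients: the drug follows diagnosis, and neither group is untreated.
- Patients who stop the drug but remain in follow-up (section 8): a self-selected group, not a randomised control.
- Exploratory moderators in 9.5.1: medication is not among them, and adding it would not create an untreated group.

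**What testing enhancement would take (illustration only).** Assume a randomised 2×2 of visit by active drug versus none, with the plan's SDs in every cell and no gain from covariates. The interaction has standard error SD × √(4/n per cell). With 60 patients, 15 per cell, √(4/15) = 0.5164 is twice √(2/30), so the normal-approximation MDDs double to 2.17, 2.89 and 3.62. Power for an interaction of 1.10 at SD 1.5 is Φ(1.10/0.775 − 1.960) = Φ(−0.54), about 29%. For 80% power, n per cell = 4 × (1.5 × 2.802/1.10)² = 58.4, so 59 per cell and 236 in total. Over the three SDs the total is 232 to 236.

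**The case against.** The best reply is that augmenting a medication's effects can simply mean a better outcome on top of medication. No section mentions an interaction or synergy, and the 9.1 design sentence names the comparator actually used. On that reading the design fits the aim. The primary hypothesis, outcome definition, ANCOVA and detectable-difference table all agree with one another.

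Much of this stands. The looser reading is open for the Précis, 1.1 and the 9.1 sentence. It is hard to sustain for 2.2, which announces a formal test that visits enhance benefits attributed to the medication. The documents therefore hold two different questions, and only one can be answered.

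A reader might also infer that an additive visit effect explains a positive result equally well, or that the plan has already established one. Neither follows. Being unable to separate two components says nothing about their relative likelihood. Section 12.1 says only that prior data suggest "a therapeutic encounter such as the expanded visit can result in at least temporary symptom improvement for some individuals"; it does not say this was independent of medication, and 2.2 notes that many pilot patients were already taking GERD drugs. An additive effect is a live alternative on the plan's own account, no more.

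**Conclusion.** The point holds as one of interpretation. The trial validly estimates the effect of the expanded versus the standard visit in patients who are all medicated. It carries no information on how that effect divides between an independent visit effect and enhancement of the drug. The 1.10-point example illustrates this; it is not an error in any planned number.

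A reader might go further and conclude that the primary analysis is invalid or the sample size wrong. The documents do not support that: the 9.1 primary hypothesis is testable as planned, and its detectable differences reproduce. The aim is unanswerable only under the stronger reading of augmentation, which 2.2 clearly adopts and the other passages permit.

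The conclusion rests on there being no placebo or untreated arm, as sections 4.3, 5.1 and 5.3.2 indicate. The 2×2 sample sizes depend on the assumptions given with them, and the conclusion does not rest on them.

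**What to change.** Align five places with the 9.1 primary hypothesis: the Primary Aim and the Design and Outcomes paragraph in the Précis, section 1.1, the hypothesis sentence in 2.2, and the design sentence in 9.1. Suggested wording: to determine whether an expanded visit, compared with a standard visit, leads to greater improvement in GERD symptoms over 8 weeks in patients who all receive study medication (amitriptyline or omeprazole according to diagnosis).

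The text should not say that the arms receive the same medication. The drug follows diagnosis and randomisation is stratified by provider only, so nothing ensures the same drug mix in each arm.

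Add one sentence to 9.5.1: a positive primary result will be interpreted as a benefit of the expanded visit among medicated patients, and not as enhancement of the drug effect itself, which this design cannot separate from an additive visit effect.

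The cost is a wording amendment and a narrower claim. Randomisation, sample size, data collection and the ANCOVA are unchanged. A factorial redesign is not proposed.
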